4. STATISTICAL ANALYSIS METHODS

4.1. Subject Disposition and Analysis Populations

An overall disposition for all subjects who sign the main Informed Consent will be summarized by investigational sites and overall. The number of subjects who are screen-failures and the reasons for screen failures will be listed. Subjects are considered as screen failures if they sign the main Informed Consent but cannot finish screening or are ineligible based on those assessments. For subjects who prematurely discontinue from the study, the premature discontinuation reasons will be summarized. For subjects who are in the ITT population, a summary table will be provided by group and overall that includes the number of subjects who reach each of the following milestones: initiated mobilization or BMH, initiated myeloablative conditioning, infused with drug product, achieved NE, achieved PE, prematurely discontinued from the study, and completed the Month 24 Visit.

Analysis populations, such as ITT, TP, SEP, and TPVOE, will be summarized in a table by group and overall. A listing of analysis populations will also be provided, and the listing will include subject ID, investigational site, the Group assigned and whether the subject is in these analysis populations (Yes/No).

4.2. Demographics and Baseline Characteristics

For subjects in the ITT population, demographic and baseline characteristics will be summarized by group and overall using descriptive statistics. Details will be presented in by-subject listings. Baseline information, such as annualized number of VOEs, sVOEs, frequency and volume of pRBC transfusions in the 24 months prior to Informed Consent will also be summarized for the applicable analysis population in the corresponding efficacy endpoints.

4.2.1. Demographics

The following demographics categories will be summarized:

- Age (in years) at the time of Informed Consent or Assent (if relevant), and age groups (≥ 12 to < 18 versus ≥ 18 to ≤ 50)
- Country of birth, sex, race, and ethnicity
- Body mass index (BMI, kg/m^2) and BMI groups (< 18.5 , ≥ 18.5 and < 25.0 , ≥ 25.0 and < 30.0 and ≥ 30.0)

Demographics tables will be repeated for the TP and TPVOE.

4.2.2. SCD-specific medical history:

The following SCD-specific medical history categories will be summarized:

- age (in years) at SCD diagnosis
- previous hydroxyurea (HU) use, including history of HU intolerance or failure
- previous L-glutamine use (Yes/No)
- previous iron chelator use (Yes/No)

- baseline VOEs and sVOEs, defined as annualized number of VOEs and sVOEs occurring in the 24 months prior to Informed Consent
- age (in years) at the time of starting regular transfusion if it is applicable
- only for Group C subjects: baseline pRBC transfusions, defined as annualized frequency and volume (in mL/kg) of pRBC transfusions received in the 24 months prior to Informed Consent
- baseline total Hb, as defined in [Section 1.2.6.2](#)
- SCD genotype (include alpha-globin and beta-globin genotypes as available)
- TRJV status at baseline (< 2.5 m/sec versus \geq 2.5 m/sec)

4.2.3. Medical History

Medical history will be coded using Medical Dictionary for Regulatory Activities ([MedDRA], Version 23.0 or higher). Medical history will be presented in a listing and summarized by Primary System Organ Class (SOC) and Preferred Term (PT).

4.2.4. Prior and Concomitant Medication and Procedures

Prior and Concomitant Medications and Procedures will be coded using the WHO DRUG (March 2016 version or higher). Medications will be provided in tables and listings, according to the intervals as mentioned in [Section 3.11](#), with an additional category, “< ICF”.

4.3. Mobilization/BMH, Conditioning and Drug Product Infusion

4.3.1. Mobilization/BMH

Mobilization/BMH details to be summarized by group or by type of stem cell collection procedure (plerixafor mobilization and apheresis, or bone marrow harvest, as appropriate):

- For subjects who underwent BMH procedure
 - Number of BMH procedures
 - Nucleated Cells Harvested ($10^8/\text{kg}$) per BMH procedure and total
 - Number of CD34+ cells collected ($\text{cells} \times 10^6/\text{kg}$) per BMH procedure and total
 - CD34+ cells cryopreserved for rescue ($10^6/\text{kg}$) per BMH procedure
 - Total nucleated cells cryopreserved for backup ($10^8/\text{kg}$) per BMH procedure
- For subjects who underwent mobilization:
 - Total number of mobilization cycles
 - Number of apheresis procedures per mobilization cycle
 - Blood volume (mL) processed per apheresis day, per mobilization cycle, and total
 - Plerixafor (mg/kg) used per apheresis day, per mobilization cycle, and total
 - Number of CD34+ cells collected ($\text{cells} \times 10^6/\text{kg}$) per apheresis day, per mobilization cycle, and total
 - Total number of CD34+ cells sent for transduction ($\text{cells} \times 10^6/\text{kg}$)
 - Total number of CD34+ cells collected for rescue ($\text{cells} \times 10^6/\text{kg}$)

Additional parameters such as amount of anticoagulant, volume of anticoagulant in bag at end of collection, and hematopoietic progenitor cells collected by apheresis (HPC-A) volume will be provided in listings.

4.3.2. Busulfan Conditioning

Busulfan conditioning details to be summarized by group include the following:

- The total dose of busulfan (mg) infused
- The average daily dose of busulfan (mg/kg/day)
- The daily estimated average area under curve ([AUC], $\mu\text{M} \times \text{min}$), which is estimated as the average AUC including both collected and derived AUC, where derived AUC is calculated as the average of the collected AUCs from CRF per busulfan dose multiplied by busulfan dose when AUC is missing but the busulfan dose is collected. If busulfan is administered as every 6 hours (Q6H), the AUC on each conditioning day will be summed first before the daily AUC calculation.
- Time (in months) from informed consent to initiation of stem cell collection
- Time (in months) from informed consent to initiation of conditioning
- Time (in months) from initiating of stem cell collection to initiation of conditioning

4.3.3. Drug Product (DP) Infusion

Drug product infusion details and the corresponding events to be summarized by group include the following:

- Time (in months) from Informed Consent to drug product infusion
- Time (months) from initiation of stem cell collection to drug product infusion
- Duration of hospitalization for conditioning and drug product infusion: defined as relative days from initiation of conditioning to post-drug product infusion discharge
- Number of drug product (DP) lots infused
- Total number of infused CD34+ cells ($10^6/\text{kg}$): combined total number of cells if more than one drug product lot. If total number of infused CD34+ cells in any individual drug product lot is reported as anomalous, the total number of CD34+ cells for the subject will not be calculated.
- Weighted average DP VCN (c/dg): weighted average per subject if more than one drug product lot infused, with weight based on the fraction of CD34+ cells in the lot/total CD34+ cells for all lots for the subject. If total number of CD34+ cells is not available, a simple average of DP VCN will be used.
- Weighted average DP %LVV+ cells (percent lentiviral vector positive cells in DP): weighted average per subject if more than one drug product lot infused, with weight based on the fraction of CD34+ cells in the lot/total CD34+ cells of all lots for the subject. If total number of CD34+ cells is not available, a simple average of DP % LVV+ cells will be used.

- Weighted average of DP VCN/DP %LVV+ cells: weighted average per subject if more than one drug product lot infused, with weight based on the fraction of CD34+ cells in the lot/total CD34+ cells of all lots for the subject. If total number of CD34+ cells is not available, a simple average of DP VCN/DP %LVV+ cells will be used.

4.4. Efficacy Analysis

The analysis populations for the efficacy endpoints identified below can be found in [Table 3](#). Listings will be provided for all efficacy endpoints. Supportive figures will be provided as needed.

The definitions of investigator VOEs, protocol VOEs, adjudicated VOEs, protocol sVOEs, and adjudicated sVOEs are listed in [Appendix 6.4, Table 14](#). All sVOE or VOE-related efficacy endpoints will be based on adjudicated sVOEs or adjudicated VOEs among Group C subjects in the TPVOE, with a 95% CI estimated for applicable binary endpoints; Supplementary analyses may also be performed based on protocol sVOEs, protocol VOEs or investigator VOEs. The endpoints will also be presented for Groups A and B subjects in the TPVOE without 95% CI estimated for the binary outcomes.

For Hb fraction analysis, the globin sample (within the analysis visit window) and the hematology sample will be merged by date. If the dates match, this Hb will be selected, even if a transfusion occurs on the same date. If a globin sample exists but there is no corresponding hematology sample with the same date, then the globin sample will be merged with the closest Hb result with no transfusion between the globin and hematology sample. If there are multiple Hb records on the same date, the one with the lowest value will be used. If the selected Hb is not within a ± 7 day window of the globin sample, the fraction will be footnoted in the data listings. An analysis visit window will be applied for by visit summary tables and figures (see [Appendix 6.2, Table 12](#) for analysis visit window). If there are multiple fractions for a subject within a given analysis visit window, an average of the fractions and Hb used to derive the fractions will be calculated and included in summary tables and figures.

The estimands for the primary and key secondary efficacy endpoints can be found in [Table 4](#).

Table 4. Estimands for Primary and Key Secondary Efficacy Endpoints

	Primary Efficacy Estimand	Key Secondary Efficacy Estimand	Key Secondary Efficacy Estimand
Treatment	bb1111	bb1111	bb1111
Population	Group C subjects in TPVOE (Group C evaluable subjects in TPVOE- for interim analysis)	Group C subjects in TPVOE (Group C evaluable subjects in TPVOE- for interim analysis)	Group C subjects in TP (Group C evaluable subjects in TP- for interim analysis)
Endpoint (variable)	Complete resolution of adjudicated VOEs between 6 months and 18 months after drug product infusion (i.e., VOE-CR)	Complete resolution of adjudicated severe VOEs between 6 months and 18 months after drug product infusion (i.e., sVOE-CR)	Globin Response, as defined in Section 1.2.6.2
Intercurrent event (ICE)	Discontinues from the study before reaching the 18th month follow-up post-drug product infusion will be considered as a non-responder.	Discontinues from the study before reaching the 18th month follow-up post-drug product infusion will be considered as a non-responder.	Discontinues from the study before achieving Globin Response will be considered as a non-responder. pRBC transfusion is considered an intercurrent event. Starting \geq 60 days after last pRBC transfusion, a subject should meet Globin Response for a continuous period of at least 6 months after drug product infusion.
Population-level Summary	Proportion of subjects achieving VOE-CR among the subjects who are in the analysis population	Proportion of subjects achieving sVOE-CR among the subjects who are in the analysis population	Proportion of subjects achieving Globin Response among subjects who are in the analysis population

4.4.1. Analysis of Primary Efficacy Endpoint

Analysis for Group C

The primary efficacy endpoint, VOE-CR, is defined as the complete resolution of adjudicated VOE between 6 months and 18 months after drug product infusion. The analysis population can be found in [Table 4](#).

Responders of VOE-CR are subjects who do not have any adjudicated VOEs between 6 months and 18 months (i.e., 183 to 548 days) after drug product infusion.

Non-Responders of VOE-CR are subjects who meet any of the following criteria:

- Has ≥ 1 adjudicated VOE between 6 months and 18 months after drug product infusion. If a subject has an adjudicated VOE that occurs before 183 days but ends after 183 days after drug product infusion, the subject is considered as a non-responder.
- Discontinues from the study on or before 18 months follow-up post-drug product infusion.

The percentage of subjects who achieve VOE-CR will be presented with a 2-sided exact 95% CI using Clopper-Pearson method for the binomial distribution. The success criterion will be at least 21 out of 35 subjects achieving VOE-CR (i.e., rate of VOE-CR $\geq 60\%$), giving a lower bound of the 95% CI greater than 40%, if exactly 35 TPVOE subjects in Group C. If there are fewer than 35 subjects in the analysis population, with the same assumptions such as the null hypothesis as 40% and alternative hypothesis as 80%, the power and success criterion can be found in [Appendix 6.3, Table 13](#).

Supplementary Analyses for Group C

The following Supplementary analyses, but not limited to, will be conducted:

Analysis Population	Supplementary Analysis
TPVOE ^[1]	The primary analysis will be repeated using protocol VOE instead of adjudicated VOE.
TPVOE ^[1]	The primary analysis will be repeated using investigator VOE instead of adjudicated VOE.

Analysis Population	Supplementary Analysis
TPVOE ¹¹⁾	
Non-Responders of VOE-CR are subjects who meet any of the following criteria:
 
• Has ≥ 1 adjudicated VOE between 6 months and 18 months after drug product infusion. If a subject has an adjudicated VOE that occurs before 183 days but ends after 183 days after drug product infusion, the subject is considered as a non-responder.• Has any death related to VOE (adjudicated by independent committee) or drug product/study procedure (assessed by investigator) on or before 18 months post-drug product infusion. 
Subjects in the TPVOE who don't meet any of the non-responder criteria above will be excluded from the analysis if they discontinued from the study on or before reaching 18 months post-drug product infusion.
 
If there is no death or discontinuation on or before 18 months post-drug product infusion, the results will be the same as for the primary analysis of VOE-CR, so this supplementary analysis will not be performed in this case.

¹¹⁾ If an interim analysis is performed, subjects should also have or would have at least 18 months of follow up post-drug product infusion.

Analysis for Groups A and B

The number and percentage of subjects achieving VOE-CR will be reported by group for Groups A and B subjects in TPVOE at final analysis, or in TPVOE who have or would have 18 months follow-up at interim analysis. No 95% CI will be presented given the relatively small sample size.

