Hydroxyurea (HU) has been helpful in a subset of patients only, with response rates of approximately 40% to 50% ([Ma et al. 2007](#)). Patients who respond show a decrease in the rate of pain and ACS events ([Charache et al. 1995](#); [Steinberg et al. 1997](#)), and beneficial findings in other organs have also been reported ([Hankins et al. 2008](#)). Hydroxyurea is a well-tolerated medication with few significant short-term toxicities; e.g., transient and reversible myelotoxicity, occasional gastrointestinal discomfort, nail or skin hyperpigmentation, and skin ulceration. However, HU is a chemotherapeutic drug; and given its primary mechanism of action and in vitro reports as a clastogen, mutagen, teratogen and carcinogen, the long-term safety profile of HU treatment in SCD remains an ongoing concern ([McGann and Ware 2011](#)). Although most studies to date have confirmed the beneficial role of HU in preventing VOEs and ACS in all age groups, the inferiority of HU in patients with stroke and chronic transfusions has been established ([Ware and Helms 2012](#)). Importantly, HU is a palliative, but not a curative, treatment modality, and studies assessing the utilization of HU in patients with SCD have identified patient compliance as a barrier to its use and efficacy ([Brandow and Panepinto 2010](#)). While there is some non-randomized evidence that patients treated with HU may live longer than those not treated with HU, patients treated with HU still experience SCD complications and, unfortunately, still die of their disease ([Bakanay et al. 2005](#); [Voskaridou et al. 2010](#)).

Adakveo (crizanlizumab) is a humanized IgG2 kappa monoclonal antibody against P-selectin that blocks interactions between endothelial cells, platelets, red blood cells, and leukocytes. It is indicated to reduce the frequency of VOCs in adults and pediatric patients aged 16 years and older with SCD ([Adakveo PI, 2019](#)). Adakveo does not impact the pathophysiological basis of the disease but is designed to reduce a specific symptom of the disease, namely pain due to vaso-occlusive disease. Efficacy was evaluated in the pivotal study and Adakveo demonstrated a lower median annual rate of VOC compared to placebo (1.63 versus 2.98); however, VOC often persisted despite treatment. Thus, it could not be considered a potentially curative therapy and symptoms often persist despite treatment.

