Anti-seizure prophylaxis must begin at least 12 hours before initiating busulfan and must continue for at least 24 hours after completion of the 4 days of busulfan administration. All drugs other than phenytoin are allowed for anti-seizure prophylaxis.

After completion of the 4-day course of busulfan, there must be a minimum of 48 hours before drug product infusion. Busulfan levels will be measured 48 and 72 hours after final dose of busulfan for retrospective confirmation of adequate wash-out.

On Day 1, bb1111 will be administered after thawing via IV infusion.

Stage 4 – Follow-up, for approximately 24 months after drug product infusion

Subjects will be followed in the hospital for AEs, and laboratory parameters will be followed to monitor engraftment. The subject may be discharged after neutrophil engraftment occurs ($\geq 0.5 \times 10^9$ ANC/L for 3 consecutive measurements on different days after the initial post-infusion nadir) and the subject is considered medically stable per institutional guidelines.

From drug product infusion through hospital discharge after neutrophil engraftment, subjects are to be medically managed with the goal of maintaining the following hematologic targets:

- Hb 8 to 10 g/dL (not to exceed 12 g/dL), HbS $< 30\%$ and
- platelet count $\geq 50 \times 10^9/\text{L}$.

After discharge, management of transfusions for subjects with SCD will follow the institutional standard of care at the clinical site to achieve total Hb and HbS proportions appropriate for each subject's clinical status. To achieve this, the transfusion program may be progressively reduced

as the contribution of Hb containing $\beta^{\text{A-T87Q}}$ -globin rises. Continued transfusion needs > 6 months post-treatment or any alternative plans should be discussed with the Medical Monitor.

Subjects will be followed in this protocol through the Month 24 Visit. Thereafter, subjects are expected to enroll in a separate, non-interventional, long-term follow-up protocol that will assess safety and efficacy beyond Month 24 for a total of 15 years after drug product infusion. The end of Study HGB-206 will be defined as the last visit for the last subject.

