5.8.2. Concomitant Medications and Therapies

All concomitant medications and therapies (i.e., those that are taken by the subject after signing the informed consent form [ICF]) should be documented.

Instructions and/or restrictions regarding specific concomitant medications and therapies are listed below. Concomitant medications and therapies not explicitly listed below may be used at the discretion of the treating physician and as per local standard of care.

- Granulocyte colony stimulating factor (G-CSF): G-CSF should not be used prior to Day 43 without explicit approval from the bluebird bio Medical Monitor.
- Venous access: Subjects will have appropriate long-term central venous access placed, per institutional standard practice, prior to beginning the preparative regimen. For subjects planned to undergo apheresis, placement of central venous access prior

to the first dose of plerixafor is strongly advised. For access, a double lumen tunneled catheter is recommended.

- Hydroxyurea: Hydroxyurea must be discontinued at least 30 days prior to stem cell harvest. It may be restarted between completion of the stem cell harvest(s) and admission to the hospital for myeloablation but should be stopped again at least 2 days before initiating myeloablation. Following HSC transplant, HU is not permitted without prior discussion with and explicit approval of the Sponsor's Medical Monitor.
- Erythropoietin: Erythropoietin is excluded and must be discontinued 60 days prior to stem cell harvest, as it may prevent engraftment of the transduced cells. Following HSC transplant, erythropoietin is not permitted without prior discussion with and explicit approval of the Sponsor's Medical Monitor.
- L-glutamine, crizanlizumab, and voxelotor: Following HSC transplant, medications other than blood transfusions to treat sickle cell disease or anemia (e.g., HU, erythropoietin, L-glutamine, crizanlizumab, voxelotor) are not permitted without prior discussion with and explicit approval of the Sponsor's Medical Monitor.

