prior to and (if possible) within 48 hours of transfusion. Subjects are recommended to continue transfusions during the pancytopenia phase to maintain Hb \geq 8 g/dL. For subjects who were on a chronic transfusion regimen prior to study entry, once engrafted and discharged post-transplant, it is recommended that the frequency of routine pRBC transfusions be adjusted to maintain Hb \geq 8 g/dL. Simple transfusions are recommended during this phase of follow-up and the period between transfusions will gradually be increased while maintaining safe HbS levels. Continued transfusion needs $>$ 6 months post-treatment or any alternative plans should be discussed with the Medical Monitor. Following HSC transplant, medications other than blood transfusions to treat sickle cell disease or anemia (e.g., HU, erythropoietin, L-glutamine, crizanlizumab, voxelotor) are not permitted without prior discussion with and explicit approval of the Sponsor's Medical Monitor.

- Platelet transfusion parameters: during the hospitalization for transplantation, platelets should be transfused to maintain a platelet count of $>$ 50,000/ μ L until platelet engraftment. After hospital discharge, subjects should get platelet count monitored approximately weekly and at least 8 days after the most recent platelet transfusion until platelet engraftment. Platelet engraftment is defined as 3 consecutive platelet count laboratory values \geq $50 \times 10^9/L$ obtained on different days while no platelet transfusions administered for 7 days immediately preceding and during the evaluation period. The day of platelet engraftment is the first day of the 3 consecutive platelet measurements.
- Blood pressure in patients with SCD is often lower than "normal" for age. Subjects should be closely monitored and antihypertensive medications started at the earliest sign of hypertension to maintain blood pressure (both systolic and diastolic) within 20% of the baseline.
- Other concomitant therapies during conditioning may include hyperdiuresis, prophylactic or therapeutic administration of anti-emetics, and veno-occlusive disease prophylaxis, e.g., ursodeoxycholic acid.
- See also next [Section 5.8.3](#) for infection prophylaxis.

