4.4.2. Analysis of Key Secondary Efficacy Endpoints

4.4.2.1. Adjudicated sVOE-CR

Analysis for Group C

One of the key secondary efficacy endpoints, sVOE-CR, is defined as the complete resolution of adjudicated sVOE between 6 months and 18 months after drug product infusion. The analysis population can be found in [Table 4](#).

Responders of sVOE-CR are subjects who do not have any adjudicated sVOEs between 6 months and 18 months (i.e., 183 to 548 days) after drug product infusion.

Non-Responders of sVOE-CR are subjects who meet any of the following criteria:

- Has ≥ 1 adjudicated sVOE between 6 months and 18 months after drug product infusion. If a subject has an adjudicated sVOE that occurs before 183 days but ends after 183 days after drug product infusion, the subject is considered as a non-responder.
- Discontinues from the study on or before 18 months follow-up post-drug product infusion

The percentage of subjects who achieve sVOE-CR will be presented with a 2-sided exact 95% CI using Clopper-Pearson method for the binomial distribution. The success criterion will be at least 24 out of 35 subjects achieving sVOE-CR (i.e., rate of sVOE-CR $\geq 69\%$), giving a lower bound of the 95% CI greater than 50%, if exactly 35 TPVOE subjects in Group C. If there are fewer than 35 subjects in the analysis population, with the same assumptions such as the null hypothesis as 50% and alternative hypothesis as 85%, the power and success criterion can be found in [Appendix 6.3, Table 13](#).

Supplementary Analyses for Group C

The following Supplementary analyses, but not limited to, will be conducted:

Analysis Population	Supplementary Analysis
TPVOE ^[1]	The analysis will be repeated using protocol sVOE instead of adjudicated sVOE.

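### SAP 3.2 allows a hematologic malignancy diagnosed before Day 183 to be scored as a VOE-CR or sVOE-CR response

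*SAP*

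**What the plan says.** SAP 4.4.1, primary endpoint: "Responders of VOE-CR are subjects who do not have any adjudicated VOEs between 6 months and 18 months (i.e., 183 to 548 days" after infusion. SAP 4.4.2.1 uses the same form for the key secondary endpoint: "Responders of sVOE-CR are subjects who do not have any adjudicated sVOEs between 6 months and 18 months (i.e., 183 to 548 days" after infusion. Each section gives two ways to be a non-responder. One is an adjudicated event in the window, including one that starts before Day 183 and runs past it. The other is leaving the study by 18 months. In SAP Table 4, discontinuation is the only intercurrent event listed for these two endpoints: "Discontinues from the study before reaching the 18th month follow-up post-drug product infusion will be considered as a non-responder".

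SAP 3.2 (General Methods) deals with a treated subject who develops a hematologic malignancy, under rules that may apply:

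- Efficacy tables and figures use data up to the date of diagnosis.
- For period-based proportions such as VOE-CR and sVOE-CR, an evaluable subject is a non-responder when the malignancy falls within the endpoint period.
- Safety analyses use data through the end of the study.

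SAP 3.12 (Interim Analyses) limits VOE-CR and sVOE-CR to Group C TPVOE subjects with actual or potential follow-up of at least 18 months. Protocol 7.4.4.1 has a similar condition. Neither mentions malignancy.

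SAP 4.4.3.3 defines sVOE-CR24 over Day 183 to Day 731 or the Month 24 visit, whichever is earlier, and derives VOE-CR24 in a similar way.

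**The concern.** The endpoint period opens at Day 183, but a malignancy can be diagnosed from infusion onward. The data cut acts at any diagnosis date, while the non-response rule acts only from Day 183. Between infusion and Day 183 the cut therefore applies alone. It removes every event that could make the subject a non-responder and puts nothing in its place.

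The outcome concerned is a named safety endpoint (insertional oncogenesis) and a trigger for urgent safety review in Protocol 3.5.4. It should not be possible to score it as a treatment success. This is a single-arm comparison with a fixed null rate, so a subject scored this way goes straight into the numerator of the only reported rate.

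**Working it through.** **1. The plan's own figures.** Inputs are from SAP 3.1: n = 35, one-sided alpha 0.025. VOE-CR has null 40%, planned rate 80% and threshold 21. sVOE-CR has null 50%, planned rate 85% and threshold 24. The method is the exact binomial tail with Clopper-Pearson limits.

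- VOE-CR: P(Bin(35, 0.40) ≥ 21) = 0.0133; P(Bin(35, 0.80) ≥ 21) = 0.998; lower limit at 21/35 = 42.1%.
- sVOE-CR: P(Bin(35, 0.50) ≥ 24) = 0.0205; P(Bin(35, 0.85) ≥ 24) = 0.996; lower limit at 24/35 = 50.7%.

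These agree with the plan, so the thresholds are sound. The gap lies in the responder rule.

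**2. The rule by date of diagnosis.** The subject is assumed to stay on study with no VOE straddling Day 183.

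| Diagnosis | Data left after the SAP 3.2 cut | SAP 3.2 non-response rule | Score under SAP 4.4.1 / 4.4.2.1 |
|---|---|---|---|
| Infusion to Day 182 | Nothing from the window | Not triggered | No analysed event, neither criterion met: responder |
| Day 183 to 548 | Window data up to diagnosis | Triggered | Non-responder |
| After Day 548 | Whole window | Not triggered | Decided by observed events |

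The first row is the anomaly. The earlier diagnosis scores better than the later one, even if VOEs occur in the window after it.

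**3. Whether other text closes the gap.**

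- *Discontinuation.* It would give non-response, but SAP 3.2 itself takes safety data through the end of the study, so it provides for follow-up after diagnosis.
- *Evaluability.* The only definition (SAP 3.12, with Protocol 7.4.4.1) is actual or potential 18-month follow-up, which such a subject can satisfy.
- *The permissive wording.* If the rules are not applied, there is no cut and events in the window count as usual. A subject with malignancy and no VOE is then still a responder.

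**4. Related endpoints.** VOE-CR24 and sVOE-CR24 also open at Day 183 and share the gap. sVOE-75 counts from infusion, so its period leaves no such interval.

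**5. Size.** Each affected subject moves the rate by 1/35 = 2.9 points.

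| Endpoint | At threshold | One fewer responder |
|---|---|---|
| VOE-CR | 21/35: lower limit 42.1%, p = 0.013 | 20/35: lower limit 39.4%, p = 0.030 |
| sVOE-CR | 24/35: lower limit 50.7%, p = 0.020 | 23/35: lower limit 47.8%, p = 0.045 |

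One recoded subject changes the conclusion only at exactly 21/35 or 24/35. At the planned rates the margin is wide: 0.80 × 35 = 28 and 28 − 21 = 7 recodings; 0.85 × 35 ≈ 30 and 30 − 24 = 6 recodings.

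SAP Table 1 shows 36 Group C subjects infused, so the TPVOE denominator may not be 35. The boundary then moves with n (SAP Table 13 covers 29 to 35).

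**The case against.** The best reply is that this is an ambiguity and not a settled scoring rule. The malignancy rules only may apply. The word evaluable could be meant to exclude such a subject, and it is defined only in the interim section. Protocol 3.5.4 says treated subjects continue, but it says so in the context of suspending enrollment. Protocol 4.5 allows withdrawal for a medical condition, and withdrawal by Month 18 is non-response. All of this stands. A reader might infer that the SAP will always score an early malignancy as success, and the documents do not support that. They support the narrower statement that the text permits it and that nothing in the text prevents it.

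A reader might also infer that ignoring transfusion and SCD drugs in the same window is an error. The ingredients are there. In Table 4, "pRBC transfusion is considered an intercurrent event" only for Globin Response. The protocol foresees later transfusion ("Continued transfusion needs > 6 months post-treatment or any alternative plans should be discussed with the Medical Monitor"; "the period between transfusions will gradually be increased while maintaining safe HbS levels"). It restricts HU without barring it ("HU is not permitted without prior discussion with and explicit approval"), and says of HU that "Patients who respond show a decrease in the rate of pain and ACS events". The inference still fails:

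- Counting event-free subjects as responders whatever else they received is in effect a treatment-policy rule. It is determinate and defensible.
- The list of supplementary analyses is open.
- Inclusion Criterion 7 requires HU failure or intolerance, and Protocol 1.1 reports no VOE difference for voxelotor.
- If one of 35 subjects were VOE-free only because of other therapy and the rest were at the null, the chance of reaching 21/35 would go from 0.013 to 0.021. That is not a type I error for the SAP's estimand, under which such a subject is a response.

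**Conclusion.** The point holds as a gap in a stated rule. With the SAP 3.2 cut applied, a subject with a hematologic malignancy diagnosed before Day 183 can enter the primary and key secondary numerators as a responder. This assumes that the subject stays on study through 18 months, has no VOE straddling Day 183, and is not excluded under an unstated meaning of evaluable.

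The numerical effect is small: 2.9 points per subject at n = 35, decisive for one subject only at 21/35 or 24/35. The documents give no count of early malignancies, and it may be zero. The reason to act is that the rule gives the wrong answer for a serious outcome and costs one sentence to correct. The handling of transfusion and SCD drugs is not part of this conclusion.

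**What to change.** In SAP 3.2, change may apply to will apply. State that a hematologic malignancy at any time from infusion through the end of the endpoint window counts as non-response: Day 548 for VOE-CR and sVOE-CR, and the end of the Month 24 window for VOE-CR24 and sVOE-CR24. Because SAP 5.2 shows that an interim clinical study report has already been produced, label this as a conservative change to the responder rule made after it, not as pre-specified. No clinical rule changes.

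The cost is that the rate may fall by 1/35 per affected subject. With one of 35 affected and the rest at the planned rate, power is P(Bin(34, 0.80) ≥ 21) = 99.6% for VOE-CR and P(Bin(34, 0.85) ≥ 24) = 99.1% for sVOE-CR.

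As an optional addition only, the sponsor could tabulate VOE-CR and sVOE-CR with subjects who had a pRBC transfusion or an SCD-modifying drug on Days 183 to 548 counted as non-responders. The primary handling would stay unchanged. It should be called a worst-case bound, with the count and the recorded indication listed by responder status, and with no claim about type I error. It should use recorded end dates. SAP Table 11 sets a missing end date for prior or concomitant treatment to data cut-off or end of study, which could wrongly flag a drug taken only before transplant.
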